| divergent validity, and discriminative validity are supported (Harrington, | | | | | | |
| 2005). | | | | | | |
| Dot Tracking Task: Will be used to manipulate participants' attentional | X | | | | X | X |
| demands. During this task, participants are presented with 12 dots on a | | | | | | |
| computer screen, 3 of which are initially yellow, and 9 of which are | | | | | | |
| gray. The yellow dots subsequently turn gray, and all the dots move at | | | | | | |

| random around the screen. When they come to a stop, participants are to remember which dots were initially yellow. There are a total of 12 trials that increase in difficulty. During the task, respiration, pulse plethysmograph, heart rate and cardiac output are continually assessed. The change in these parameters from resting to that observed during dot tracking serves as an assessment of change in parasympathetic and sympathetic nervous system activation as a | | |
|--|---|---|
| function of attentional demands. The construct indexed, vagal flexibility, is linked to the ability to adaptively respond to stress (Muhtadie, Koslov, | | |
| Akinola, & Mendes, 2015). | | |
| Smoking Abstinence Expectancies Questionnaire (SAEQ): 28-item self-report questionnaire evaluates the the expected short-term psychological and physiological consequences of abstaining from smoking. Full-scale and subscale (Negative Mood, Somatic Symptoms, Harmful consequences and Positive Consequences) scores exhibit good internal consistency, convergent and discriminant validity, and test-retest reliability (Abrams, K., Zvolensky, M., Dorman, L., Gonzalez, A., & Mayer, M. (2011). | X | X |
| Barkley Deficits in Executive Functioning Scale-Short Form (BDEFS-SF): 20-item short form of the BDEFS assessing daily executive functioning, such as self-regulation of emotions and time management. Participants will use a 4-point Likert-type scale (1 = never or rarely to 4 = very often) to indicate how often they experience each statement (e.g., "Make impulsive comments to others"). This scale has demonstrated good reliability and validity (Barkley, R. A. (2011). | X | X |
| 5-Trial Adjusting Delay Task: a novel method of obtaining a delayed discount rate in less than 1 minute such that participants answer only 5 questions as a result of branch logic which generates individually tailored choice options from 31 possible items (Koffarnus, M. N., & Bickel, W. K. (2014). | X | X |
| Adult ADHD Self-Report Screening Scale (ASRS-5): 6-item measure that is short, easily scored, and can detect the vast majority of adult attention-deficit/hyperactivity disorder cases in the general population with high sensitivity and specificity. The scale has excellent cross-validated concordance with blinded clinical diagnoses of DSM-5 adult attention-deficit/hyperactivity disorder (Kessler, et al., (2005). | X | X |
| Perceived Stress Scale (PSS10): 10 item measure designed to assess stress perceptions on a 5-point Likert scale ranging from 0 = never to 4 = very often. Items were designed to tap how unpredictable, uncontrollable and overloaded respondents find their lives. Construct validity, internal reliability and predictive reliability are supported (Cohen, S., & Williamson, G. (1988). | X | X |
| Cigarette Purchase Task (CPT): 26-item measure used to assess trait demand for cigarettes or the behavior-maintaining properties of nicotine. Participants report the number of hypothetical cigarettes they would purchase for consumption across varying prices (i.e. \$0.00-9.00). This results in a curve that represents the relationship between the demand for cigarettes and escalating price. The demand curve is comprised of the following indices: intensity (number of cigarettes consumed at unrestricted cost), breakpoint (price at which consumption is suppressed to zero), Omax (peak expenditure for cigarettes), Pmax (the price at maximum expenditure for cigarettes), and elasticity (the degree to which consumption decreases with increasing price) | X | X |

| (MacKillop, et al., (2008) | | | | |
|--|--|--|--|---|
| Exit Interview: Used to collect information about the participant's | | | | X |
| understanding of the rationale for the intervention, the degree to which | | | | |
| the information was applicable and relevant, and their overall feedback | | | | |
| and thoughts on the intervention to inform adjustments to the | | | | |
| subsequent R01 trial. | | | | |
| Cotinine Sample: Biochemical verification of smoking abstinence will | | | | X |
| support point prevalence abstinence at the 3m follow-up via the | | | | |
| Salimetrics Enzyme Immunoassay Salivary Cotinine Kit. | | | | |
| Ratings of Session Protocol Adherence and Examination of | | | | X |
| Physiological Data for Intervention Accuracy: Recorded sessions | | | | |
| will be coded in order to assess accuracy of intervention delivery. | | | | |

HRVB and SCT Clinician Training and Supervision: Clinicians will receive a minimum of 8 hours of training from study investigators in the application HRVB and will have to complete a minimum of 5 practice sessions prior to seeing participants. Clinicians will be approved for the study following careful assessment of their protocol adherence, competent application of skills, by the PI. Clinicians will have to demonstrate general knowledge in appropriately modifying HRVB for participants, navigating and addressing common barriers (e.g., discomfort, dizziness), addressing motivation and adherence, instructing and monitoring participants both in-lab and virtually, and will role-play managing several common issues that arise during HRVB before they are assigned participants. Fidelity data will be collected via independent evaluators who will use an HRVB-specific rating scale to assess protocol adherence, implementation of strategies and skills in-session. Designated study assessors will be asked to code audio-recordings, specifically, 25% of the initial eight HRVB sessions provided to participants will be coded (Muse & McManus, 2013). Fidelity will additionally be assessed by Co-I [name] who will review recorded physiological data from baseline and 3-month follow up to rate whether participants, under therapist instruction, received adequate resonance between heart rate and blood pressure, central to the success of the intervention. Measures of treatment fidelity are critical to the current proposal given it has never been applied to smokers and requires ongoing monitoring of participant behavior and physiology. For example, slow-paced breathing is sometimes accompanied by compensatory changes in breath depth, a process that can inadvertently decrease end tidal carbon dioxide (etCO2), which is contraindicated and will not result in desired RSA oscillations; clinicians will need to know how to identify and remedy contraindicated breathing patterns, such as hyperventilation, both during in-lab and remote sessions, to promote accurate HRVB application.

Clinicians will additionally receive at least 5 hours of training in the delivery of SCT. SCT training will include psychoeducation regarding the prevalence of smoking, common beliefs about smoking and cessation, as well as specific training in the co-occurrence of depression and anxiety in smokers and implications for intervention. Clinicians will be trained in the administration of the adapted manual, teaching of skills to participants, conducting the intervention in-lab and virtually, and how to develop personalized smoking cessation plans. Clinicians will complete several role play sessions so that they are equipped with the various issues that commonly impede smoking cessation, and how to appropriately respond. In addition to training, clinicians will be asked to record a minimum of 3 practice sessions. Prior to being approved for the study, the PI will review for adherence to the study protocol and determine if additional training is needed. All clinicians will be provided with additional feedback following review of recorded sessions.

Clinical supervision will occur on a weekly basis with the PI for 2 hours. The first hour will be spent reviewing HRVB sessions, and the second hour will be spent reviewing SCT sessions. The purpose of supervision is to provide additional training and support to clinicians to ensure fidelity of the intervention. In addition, issues regarding homework compliance and participant retention will be addressed.

9/17/2024

Potential Problems and Alternative Strategies: Clinicians will be trained to be flexible in HRVB application depending on the needs of the patient. For example, additional use of the pacer or biofeedback may be indicated for an individual who is struggling with appropriate respiratory pacing or achieving maximal oscillations, respectively. Alternatively, both strategies may be abandoned, and the clinician may choose instead to focus on breath depth and quality, if a patient is experiencing difficulty with hyperventilation (e.g., decreases in expired tidal volume of CO₂). Because at-home practice is critical to the promotion of long-term improvements in vagal cardiac activity, the first two weeks will include both an in-person and virtual training session. To address adherence, we have put in place several strategies. Participants who do not have smart phones will be given one for use during the duration of the study. Athome practice will be characterized as a tool that participants may use in place of smoking. In this manner, participants may begin to reduce smoking and conceptualize practice as a helpful skill, rather than a time-consuming task. Such an approach is bolstered by the ease of use of the phone app, which is discreet, on their person, and will serve as a practice cue. To test feasibility of the intervention, without offering additional incentive, our participants will not receive additional adherence reinforcement.

In accord with clinical practice guidelines, participants will begin NRT on the morning of their quit date and will be provided with a full 8-week course (Fiore et al., 2008). This will ensure that assessment of ANS parameters just prior to the quit day is not confounded. Participants will not complete their taper until the end of week 6; this will allow for adequate washout of plasma nicotine, allowing us to biochemically verify abstinence and examine additional cardiac vagal tone changes as a function of treatment.

The ongoing COVID-19 pandemic places all research in an unpredictable situation. We anticipate that we may experience challenges in recruitment and retention associated with illness or safety concerns that could affect both study personnel and participants. We will address these issues on an ad hoc basis, for example, by subbing in respiratory therapists when possible, permitting participants to do make-up sessions, collecting in-person data at modified times, etc., and carefully documenting each adjustment made. Also, a growing body of empirical work has documented the extensive effects of the pandemic on mental health, including emotional distress and substance use. We have added several questionnaires, both validated quantitatively and qualitatively, to obtain information regarding the effects of the pandemic on mental health and functioning, as well as information regarding personal COVID-19 related experiences (e.g., disease contraction by self or close contact). Collection of this data will help the study team glean whether any related effects, or lack thereof, or differences in outcomes between Stage 1A and 1B may be attributable to the pandemic.

Transition to a remote intervention introduces several concerns related to intervention fidelity. Although the Inner Balance device provides relatively reliable real time HRVB feedback, therapists cannot view the participant and their physiology simultaneously. This may introduce challenges in determining whether the participant is practicing the intervention correctly and troubleshooting difficulties they are experiencing, such as feeling breathless or lightheaded. To address these concerns, the baseline appointment includes extensive training in the intervention and orientation to using the Inner Balance device and the Zoom mobile and computer software, so that participants can swiftly move between screens when working with their respiratory therapist remotely. Also, it is possible that the intervention may be disrupted due to connectivity problems. In the event this occurs, a backup plan, including the use of other HIPAA compliant platforms (e.g., Microsoft Teams), will be enacted, or the session will be moved to traditional audio phone call or rescheduled.

Compensation: Participants will receive up to \$755 in total study compensation. This includes \$10 per week for general participation, \$35 for baseline and 1-month follow-up appintments, \$50 for their 3-month follow-up appointment, a \$50 bonus for attending at least 6 out of 7 sessions. Additionally, subjects will be paid up to \$105 each week for at home breathing practice from weeks 2-6.

B. Data Points

9/17/2024

Data will be collected over the course of 15 weeks, which include 3 in-person laboratory sessions and 5 remote sessions (see *Table 1*), and will include interview, self-report, behavioral, and psychophysiological assessment.

C. Study Duration

Following the baseline and first session, which will last 1-3 hours, participants will be asked to complete 6 additional intervention sessions over the course of 6 weeks, lasting 30-60m each. They will also be asked to complete a final follow-up appointment, which corresponds with 3-months post their quit date.

D. Endpoints

N/A

1.4 Preliminary Data

Complete reporting of preliminary data collected during the Pilot Phase IA of this trial can be found under the eIRB protocol Pro2018001848. Of particular relevance for the current protocol, feasibility findings from the preliminary Phase 1A of this study suggest the previous in-person structure could be improved. Primary Phase IA outcome measures assessing intervention feasibility included participant attendance and ratings of the intervention's efficacy, appropriateness of fit, and ease of use in daily life. All scale scores ranged from 0=completely disagree to 4=completely agree. Intervention acceptability also served as a primary outcome and was assessed via participant ratings of intervention satisfaction and liking. Of the seven participants who remained in treatment beyond the first session, an average of 8.71 (SD= 1.49) treatment sessions were attended. At the 3-month follow-up visit, participant average ratings of the intervention's efficacy, appropriateness, ease of use, and acceptability were 3.19 (SD=0.52), 2.87 (SD=0.75), 1.58 (SD=0.32), and 3.52 (SD=0.31), respectively. While the intervention was high in efficacy, appropriateness, and acceptability, these initial results suggest the intervention was not perceived as being easily integrated into participant's daily lives. With this in mind, an intervention protocol modified for predominantly remote instruction may facilitate in addressing this previous feasibility limitations (see Feasibility section 4.3C for further detail).

1.5 Sample Size Justification

Given the developmental nature of the project, our sample size was selected to obtain a reasonable estimate of treatment feasibility, acceptability, and efficacy that would be critical to supporting a future R01 clinical trial. We enrolled n=10 participants for phase 1A and plan to enroll n=30 for phase 1B. Statistical power for phase 1B was determined using G*Power 3.1.9. and based on the analytic approach for examining our secondary outcomes of interest. Separate paired sample t-tests will be used to examine within-subject differences in the number of cigarettes smoked per day and in emotional distress from pretreatment baseline, 1-month post-quit, and 3-month post-quit, respectively. Paired sample t-tests determined that at a power of 80%, α =0.25, an N=30 is sufficient to detect a small to medium-sized effect (Cohen's d=0.40). A Type I error rate of .25, has been suggested as an adequate error rate for testing preliminary pilot study effects and can be used to inform a more comprehensive study, including sample size planning for a future Stage II R01 (Moore et al., 2011). Given our relatively short assessment phase, this may still be too conservative estimate. Therefore, we will carefully examine effect size estimates and pursue a larger trial if a small to medium effect is observed.

1.6 Study Variables and Outcomes

To inform a subsequent clinical trial, our analytic plan focuses on the use of descriptive and inferential statistics.

Primary Outcomes:

9/17/2024

Aims 1.a. and 1.b.: Feasibility and Acceptability:

Descriptive statistics will be used to assess feasibility and acceptability of HRVB (see 1.a. Intervention feasibility and 1.b. Intervention acceptability). Ratings of perceived effectiveness, appropriateness, satisfaction, and ease of the intervention are made on a 5-point Liker-type scale ranging from 0-completely disagree to 4-completely agree. Descriptive statistics will also be used to assess participant attendance, adherence, indexed by time spent using the intervention. Instances of technological limitations will be indexed both by count as well as qualitative descriptors (e.g., inner balance device failure to pick up recording; Bluetooth connection errors, etc.).

Secondary Outcomes:

Aim 2.a: Changes in smoking behavior:

Descriptive statistics will be used to report total number and percent of participants reporting abstinence on their quit day using the intent-to-treat sample as well as those who remain in treatment.

Sustained smoking cessation will be assessed descriptively using point prevalence abstinence defined by self-reported abstinence verified by both carbon monoxide analysis of breath sample and saliva cotinine. Paired sample t-tests will be used to assess changes in smoking rate within participants from baseline to quit day, two-week, one-month, and three-month follow-up, as a proxy for harm reduction.

Aim 2.b.: Changes in emotional distress:

Paired sample t-tests will be used to assess changes in emotional distress, including depression, anxiety and stress, within participants, from baseline to two-week, one-month, and three-month follow-up.

We will also examine correlations between baseline emotional distress ratings and key outcomes, including feasibility and acceptability ratings, changes in smoking behavior, and emotional distress to evaluate whether the intervention may be particularly beneficial for smokers with elevated emotional distress.

The following list of measures will be used to assess primary and secondary outcomes of interest:

1.a: Intervention feasibility

| Outcome | Method | Time Frame |
|------------------------|---|-------------------------------------|
| Participant Attendance | Number of attended sessions out of 7 possible | 7 weeks |
| | sessions | |
| Practice Adherence | Time (in minutes) spent practicing the breathing | 7 weeks |
| | intervention | |
| Intervention | Participant self-report items assessing how effective | Week 1 (i.e., treatment initiation) |
| Effectiveness | the intervention was in helping participants quit and | and Week 16 (i.e., 3-MFU) |
| | manage emotional distress | |
| Intervention | Participant self-report items assessing intervention | Week 1 (i.e., treatment initiation) |
| Appropriateness | comprehension and fit | and Week 16 (i.e., 3-MFU) |
| Intervention Ease | Participant self-report items assessing ease of use | Week 1 (i.e., treatment initiation) |
| | and fit into daily lifestyle | and Week 16 (i.e., 3-MFU) |
| Technological | Interventionist self-report items assessing incidences | 7 weeks |
| Limitations | of technical issues and related effects on intervention | |
| | delivery | |

1.b. Intervention acceptability

9/17/2024

| Outcome | Method | Time Frame |
|-------------------------|---|---|
| Satisfaction and Liking | Self-report items assessing satisfaction with learning the intervention, liking the intervention, breathing techniques, nicotine replacement, and recommending the intervention to others | Week 1 (i.e., treatment initiation) and Week 16 (i.e., 3-MFU) |

2. Secondary Outcome Measures:

2.a. Changes in smoking behavior

| Outcome | Method | Time Frame |
|--------------------------------|---|---|
| Quit-day abstinence | Self-reported abstinence on Quit Day, verified with carbon monoxide analysis of breath sample (CO < 8ppm) | Week 3 (i.e., Quit Date) |
| Sustained Smoking Cessation | Self-reported abstinence, verified carbon monoxide analysis, and salivary cotinine (<10 ng/mL) at study termination | Week 16 (i.e., 3-MFU) |
| Smoking rate | Timeline Followback interview assessing changes in smoking rate | Week 0 (i.e., Baseline,) Week 3 (i.e., Quit Date), 5 (i.e., 2-WFU), Week 7 (i.e.,1-MFU) and Week 16 (i.e., 3-MFU) |

2.b: Changes in emotional distress (i.e., anxiety, depression, and stress)

| Outcome | Method | Time Frame |
|--------------------|--|--|
| Emotional Distress | Self-report items assessing past 2-week ratings of depression, anxiety, and stress | Week 0 (i.e., Baseline,) Week 5 (i.e., 2-WFU), Week 7 (i.e.,1-MFU) and Week 16 (i.e., 3-MFU) |

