4.3 Number of Subjects

A. Total Number of Subjects

Up to 50 participants will be consented with a target enrollment of n = 30 who will receive a minimal dose of treatment (i.e., at least one intervention session)

B. Total Number of Subjects If Multicenter Study N/A

C. Feasibility

We have chosen to include participants ages 21-50. Although limited, this allows us to capture a large group of current daily smokers, with recent research indicating greatest declines in smoking prevalence in those ages 18-24 (Centers for Disease Control and Prevention, 2012). This also helps ensure participants have smoked regularly for several years. Research has found that autonomic parameters, including heart rate variability, (Berntson et al., 1997) blood pressure, (Cugini et al., 2003) and the baroreflex, (C. M. Brown, Hecht, Weih, Neundörfer, & Hilz, 2003) are affected by age, with significant decreases occurring in middle age. Therefore, inclusion of individuals older than 50 in this pilot study may confound treatment effects or interpretation of physiological parameters of interest. We have chosen to enroll smokers who smoke at least 5 cigarettes daily. We will exclude non-daily smokers. This will help in both feasibility as well as generalizability with recent research indicating that the proportion of heavy smokers (> 30/day) has declined to 9.1% from 12.5% between 2010 and 2011, whereas the percent who smoke between 1-9/day has increased to 22%, in the same time frame (Centers for Disease Control and Prevention, 2012). This is consistent with other reports indicating that smokers are smoking less per day, and that other indicators such as daily smoking and time to first cigarette may be better indicators of cigarette dependence (Baker et al., 2007).

Based on the preliminary feasibility findings from Phase 1A of this trial, a treatment protocol modified for predominantly remote instruction (as listed here) may yield several feasibility gains. Specifically, the reduced number of in-person study visits will mitigate participant burden (i.e., reduced time

9/17/2024

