6.4 Data Management Plan

6.5 Data Analysis

Primary analyses will use descriptive statistics to assess feasibility and acceptability of HRVB. Ratings of perceived effectiveness, appropriateness, satisfaction, and ease of intervention are made on a 5-point Liker-type scale ranging from 0-completely disagree to 4-completely agree. Descriptive statistics will also be used to assess participant attendance, adherence, indexed by time spent using the intervention. Instances of technological limitations will be indexed both by count as well as qualitative descriptors (e.g., inner balance device failure to pick up recording; Bluetooth connection errors, etc.) Secondary analyses for Aim 2.a: Changes in smoking behavior will include descriptive statistics used to report total number and percent of participants reporting abstinence on their quit day using the intent-to-treat sample as well as those who remain in treatment. Sustained smoking cessation will be assessed descriptively using point prevalence abstinence defined by self-reported abstinence verified

9/17/2024

by both carbon monoxide analysis of breath sample and saliva cotinine. Paired sample t-tests will be used to assess changes in smoking rate within participants from baseline to quit day, two-week, one-month, and three-month follow-up, as a proxy for harm reduction. Secondary analyses for Aim 2.b: Changes in emotion distress will include paired sample t-tests used to assess changes in emotional distress, including depression, anxiety and stress, within participants, from baseline to two-week, one-month, and three-month follow-up. To explore whether the intervention may be particularly beneficial for smokers with elevated emotional distress, we will examine correlations between baseline emotional distress ratings and key outcomes, including feasibility and acceptability ratings, changes in smoking behavior, and emotional distress.

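### Change in smoking rate and distress rests on separate complete-pair t-tests with no missing-data rule; a mixed model using all visits is a cheap safeguard for the effect size

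*Combined protocol and SAP*

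**What the plan says.** Section 1.6 plans for Aim 2.a: "Paired sample t-tests will be used to assess changes in smoking rate within participants from baseline to quit day", and then from baseline to two weeks, one month and three months. For Aim 2.b it plans: "Paired sample t-tests will be used to assess changes in emotional distress, including depression, anxiety and stress, within participants", from baseline to two weeks, one month and three months. Section 6.5 repeats this ("Changes in emotion distress will include paired sample t-tests used to assess changes in emotional distress"), and section 1.5 calls the tests separate. None of these sections names an analysis set for the tests or says what happens to missing values.

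Section 4.3 sets a "target enrollment of n = 30 who will receive a minimal dose of treatment (i.e., at least one intervention session", so a person who leaves after session 1 is one of the 30.

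Section 1.5 states that "an N=30 is sufficient to detect a small to medium-sized effect" (d = 0.40, 80% power, alpha 0.25). It closes by saying the team will look at effect size estimates and "pursue a larger trial if a small to medium effect is observed".

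For abstinence, section 1.6 reports quit day "using the intent-to-treat sample as well as those who remain in treatment". Sustained cessation is defined as "Self-reported abstinence, verified carbon monoxide analysis, and salivary cotinine (<10 ng/mL) at study termination", with no denominator given.

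**The concern.** A paired t-test drops anyone without the follow-up value. With no other rule stated, each 3-month comparison describes the people who came back. If those who were doing worse at 1 month are less likely to return, the average change among returners overstates the change in the 30 enrolled, and so does the d computed from it.

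This matters more than usual for secondary outcomes in a pilot because section 1.5 links an observed effect size to going ahead with a larger trial. The information that could correct much of the distortion is already scheduled: five smoking-rate assessments and four distress assessments per person (section 1.6 outcome tables). Separate pairwise tests ignore the intermediate visits.

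**Working it through.** **1. The plan's own figure.** Paired t-test, d = 0.40, alpha 0.25. Sidedness is not stated; two-sided is taken here. Power comes from the noncentral t with n − 1 degrees of freedom and noncentrality 0.40 × √n.

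- n = 30: 84.5%
- n = 26: 80.6%
- n = 25: 79.5%
- n = 21: 74.4%

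Thirty complete pairs are sufficient, as section 1.5 says, and 26 would do. Power is not the problem.

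**2. Inputs for the bias check.** The documents do not give Phase 1B retention, so 90%, 80% and 70% measured at 3 months are assumed. Section 1.4 reports seven participants who stayed beyond session 1, and section 1.5 gives ten enrolled in Phase 1A. That is a weak guide from an in-person version. Also assumed: equal SD s at every visit, correlation 0.5 between any two visits, normal data, and only the 3-month value missing.

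**3. Correlation of the two changes.** Write B for baseline and Y1, Y3 for the 1- and 3-month values.

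- Var(B − Y) = 2s²(1 − 0.5) = s²
- Cov(B − Y1, B − Y3) = s²(1 − 0.5 − 0.5 + 0.5) = 0.5s²
- The correlation is therefore 0.5.

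**4. Loss related to the observed 1-month change.** Let z be that change, centred and in SD units. Let the probability of being measured at 3 months be 1/(1 + exp(−(a + z))), with a set to give the stated retention. The mean z among those measured, times 0.5, is the shift in mean 3-month change. Dividing by a true d of 0.40 gives the relative bias of the paired estimate.

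| Measured | a | Mean z if measured | Shift (SD) | Paired bias |
|---|---|---|---|---|
| 90% | 2.564 | 0.091 | 0.045 | +11% |
| 80% | 1.650 | 0.173 | 0.087 | +22% |
| 70% | 1.018 | 0.253 | 0.126 | +32% |

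Simulations of 30 people on the same assumptions gave +30% to +33% for pairs at 70%, and within 2% of zero for an unstructured mixed model.

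**5. Data closer to cigarettes per day.** A further simulation used 33% abstinent at 1 month, 24% abstinent at 3 months, loss by observed 1-month reduction and 70% seen. Bias was +11% for pairs, +1% for the unstructured model and −23% with missing values set to baseline.

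**6. Other kinds of loss, normal data, 70% measured.**

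- Unrelated to outcome: pairs 0%, model about 0%. Set-to-baseline is 0.70 × 1.00 − 1 = −30%.
- Dependent on the unseen 3-month change: pairs 0.253/0.40 = +63%. The model gave about +40% in simulation. Set-to-baseline is 0.70 × 1.63 − 1 = +14%.
- For comparison, set-to-baseline under step 4 is 0.70 × 1.32 − 1 = −8%.

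**7. What this could do to a decision.** Section 1.5 gives no cutoff. If small to medium is taken as d ≥ 0.40, the value it labels that way, a true d of 0.20 reaches it 15.0% of the time with 30 complete pairs (noncentral t). With loss as in step 4 at 90/80/70% measured, simulation gives about 22/31/39% for pairs and 14/16/18% for the model. On complete data the two mean changes are identical, so any difference in d there comes only from how the SD is defined.

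**8. Choice of covariance.** With follow-ups correlated 0.7 with each other and 0.5 with baseline, 70% seen and loss by observed change, simulated bias was +46% for pairs, 0% for unstructured covariance and +8% for compound symmetry.

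**9. Abstinence denominator.** Six verified quitters are 6/30 = 20.0% of those enrolled, 6/24 = 25.0% of those seen at 80% retention, or 6/21 = 28.6% at 70%.

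**The case against.** *Loss may be small.* The plan allows make-up sessions and modified collection times (section 1.3, Potential Problems), pays $50 for the 3-month visit (Compensation), and keeps contacting people who miss visits (section 4.4). It offers an assessments-only route to those who want to stop (section 4.5) and uses Timeline Followback, which is retrospective (Table 2). This stands: loss may be low, and with none the methods agree. These steps reduce the number missing but give no rule for those who remain missing. Reporting participant flow (section 6.4) shows the loss without correcting the estimate.

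*The decision rule is loose.* A reader might infer that the paired effect size alone decides the larger trial. Section 1.5 does not support that. It names no outcome, visit or cutoff, and the primary outcomes are descriptive feasibility and acceptability. What remains is that the sentence directly follows the paired t-test power statement, which makes these estimates a likely input.

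*The model is not a cure.* This also stands. If people stay away because of relapse nobody observed, the model keeps about +40% bias, and set-to-baseline is closer to the truth at +14%. Set-to-baseline is badly wrong in the other direction under random loss (−30%), so neither should be shown alone.

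*The normal-data figure flatters the point.* For smoking rate, +11% is the more relevant illustration than +32%.

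**Conclusion.** The point holds as a cheap improvement to a secondary analysis. Separate paired t-tests with no missing-data rule give too favourable an effect size when 3-month loss is related to earlier change. At 70% measured the size is about +32% for normal data and about +11% for zero-heavy cigarette data, against about 0 to +1% for a mixed model. Retention, correlation and the strength of the loss mechanism are all assumed. At 90% measured the normal-data figure falls to +11%, and with loss unrelated to outcome it is zero.

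A reader might also infer a sample-size error; the documents do not support one, since 30 pairs exceed the 26 needed. Nor can either analysis isolate the effect of HRVB. The trial has one arm receiving HRVB, counselling and patches together, so d measures change under the whole package.

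The missing 3-month abstinence denominator is a reporting gap and secondary to the main point.

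**What to change.** 1. For smoking rate and for each distress scale, fit one repeated-measures mixed model using all available visits from all 30 enrolled. Use visit as a category, unstructured covariance (15 parameters for five visits, 10 for four), a named simpler structure if it does not converge, and small-sample degrees of freedom.
2. Report the model-based change at 1 and 3 months, the visits section 1.5 names, with a confidence interval, as the effect-size estimate. Scale d by the same SD definition as the paired d.
3. Keep the planned paired t-tests alongside and, for smoking rate, add a missing-set-to-baseline result. Label both as sensitivity analyses.
4. Report 3-month verified abstinence out of all enrolled, with unverified or missing counted as smoking, beside the rate in those seen, as section 1.6 already does with two denominators for quit day.

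The cost is SAP wording and modest analysis, with no new visits or instruments. The estimate may be less favourable, and the model may not converge in 30 people. Normality is only approximate when quitters contribute zeros, as it is for the paired t-test. Section 1.10 planned final follow-up by the end of June 2023 and the pages are dated 9/17/2024. If the data have already been analysed, the model must be labelled post hoc.
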